- Participants who are eligible to participate in the LTE study and have consented will continue with LTE Week 0 activities after completing Week 0 assessments and follow SoA for LTE for subsequent visits. Participants who are not eligible or do not want to participate in the LTE study will continue to Week 60 visit in the main study for final safety follow up assessments.
- FDG PET/CT is to be performed during screening prior to Week 0, and at Week 52 (or timepoint of flare if earlier). If a participant has a GCA flare prior to Week 52, an attempt will be made to perform the FDG PET/CT imaging at that flare timepoint instead of Week 52, preferably within 1 week from identification of GCA flare by the principal investigator. If FDG PET/CT scan is used for diagnosis this may be used as the study baseline image but requires sponsor pre approval. This is to avoid exposure of the participant

Schedule of Activities From Screening through Week 60

Period	Screening ^a -6 to -1	Blinded Active Treatment Period												Safety Follow-up				
		0	4	8	12	16	20	24	28	32	36	40	44	48	52 ^g	60	Flare Visit ^q	Early Termination Visit ^b
Study Week																		
Study Day (post D1 window \pm 7 days)	-42 to -1	1	28	56	84	112	140	168	196	224	252	280	308	336	364	420		
Study Procedure ^c																		

to excess radiation. FDG PET/CT scan is being obtained as part of exploratory endpoint and results should not be used in determining disease status at the associated week 52 visit.

- i. Chest radiograph (posterior anterior and lateral views, or per country regulations where applicable) must be obtained within 12 weeks before the Week 0 visit. Note: A chest CT scan is also acceptable if obtained instead of a chest radiograph outside of the protocol.
- j. At the screening visit, the C SSRS should be completed as the first assessment after signing informed consent and before any other tests, procedures, or other consultations. For subsequent visits, the C SSRS should be completed after all PROs and before any other tests, procedures, or other consultations. In this study, the C SSRS is a physician administered questionnaire and should be administered by certified, trained, and delegated principal investigator or subinvestigator only.

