3. OBJECTIVE AND ENDPOINTS

Objectives	Endpoints
Primary	
To evaluate the efficacy of guselkumab compared to placebo, in combination with a 26-week glucocorticoid (GC) taper regimen, in adult participants with new-onset or relapsing giant cell arteritis (GCA).	The proportion of participants achieving GC-free remission at Week 28
Secondary	
To evaluate the efficacy of guselkumab compared to placebo, in combination with a 26-week GC taper regimen, in adult participants with new-onset or relapsing GCA as measured by alternative definitions of GC free remission, GC-sparing effects, and prevention of disease flares.	
The proportion of participants achieving GC-free remission from Week 28 by visit through Week 52
 
The proportion of participants achieving GC-free remission and normalization of erythrocyte sedimentation rate (ESR) at Week 28 and by visit through Week 52
 
The proportion of participants achieving GC-free remission and normalization of C-reactive protein (CRP) at Week 28 and by visit through Week 52
 
The proportion of participants achieving GC-free remission and normalization of both ESR and CRP at Week 28 and by visit through Week 52
 
The cumulative GC dose through week 28 and through Week 52
 
The time to first GCA disease flare or discontinuation of study intervention due to AE of worsening of GCA through Week 28 and through Week 52
 
The number of GCA disease flares or discontinuation of study intervention due to AE of worsening of GCA through Week 28 and through Week 52

To evaluate the safety of guselkumab, in combination with a 26-week GC taper	Number/proportion of participants with treatment-emergent adverse events (TEAEs) through Week 60

Objectives	Endpoints
regimen, in adult participants with new-onset or relapsing GCA.	
Number/proportion of participants with TEAEs by system organ class with a frequency threshold of 5% or more through Week 60
 
Number/proportion of participants with treatment-emergent serious adverse events (SAEs) through Week 60
 
Number/proportion of participants with clinically significant abnormalities in vital signs, laboratory safety tests through Week 60

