FDG-PET/CT scan can be scheduled separately from other assessments. In case of subsequent flares, a Flare visit should be performed according to the SoA with the exception of the FDG-PET/CT scan. Depending on the circumstances, reduced assessments may be considered in consultation with the sponsor.

Efficacy, safety, PK, immunogenicity, and biomarkers will be assessed according to the Schedule of Activities (SoA; Section 1.3). An optional pharmacogenomic blood sample will be collected from participants who consent to the collection of these samples (where local regulations permit).

The primary efficacy analysis will be performed after all participants have completed Week 28 efficacy assessments (or discontinued). Additional secondary endpoints will be completed at Week 28 and Week 52. Three planned database locks (DBLs) will occur, at Week 28 and at Week 60 for the main study and a final DBL lock when the last participant completes last visit in the LTE period. The study will be double-blind until all participants have completed the main study and associated Week 60 DBL has occurred.

An independent DMC will be commissioned for this study. Refer to Sections 9.6 (Data Monitoring Committee) and for the Committees Structure in Section 10.3.

Long-term Extension Treatment Period (Week 52 to Week 112; optional for eligible participants)

Participants who complete the Week 52 visit and are assessed to be in GC-free remission, may have the option to participate in the LTE period of the study.

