4.4. End of Study Definition

End of Study Definition

The end of study is considered as the last visit for the participant in the study. The final data from the study site will be sent to the sponsor (or designee) after completion of the final participant visit at that study site, in the time frame specified in the Clinical Trial Agreement.

Study Completion Definition

A participant will be considered to have completed the main study if the participant has completed study treatment through Week 48 of the main study phase, and the 12-week safety follow-up for the main study (Week 60) or, if a participant continued onto the LTE period, has completed main study Week 52 visit. For the LTE period, a participant will be considered having completed the study if the participant has completed study treatment through Week 100 (LTE Week 48) and the 12-week safety follow-up for the LTE period (Week 112 [LTE Week 60]).

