f) Have a chest radiograph (both posterior-anterior and lateral views, or per country regulations where applicable), taken within 3 months before the first administration of study intervention and read by a qualified radiologist (or pulmonologist in accordance with local regulations), with no evidence of current, active TB or old, inactive TB. A chest CT scan is also acceptable if obtained instead of a chest radiograph outside of the protocol.

15. Have screening laboratory test results within the following parameters, if one or more of the laboratory parameters is out of range, a single retest of laboratory values is permitted:

a. Hemoglobin	≥ 9 g/dL	SI: ≥ 90 mmol/L
b. White blood cells	$\geq 3.0 \times 10^3/\mu\text{L}$	SI: ≥ 3.0 GI/L
c. Neutrophils	$\geq 1.5 \times 10^3/\mu\text{L}$	SI: ≥ 1.5 GI/L
d. Platelets	$\geq 100 \times 10^3/\mu\text{L}$	SI: ≥ 100 GI/L
e. Serum creatinine	≤ 1.8 mg/dL	SI: ≤ 159 $\mu\text{mol/L}$
f. Aspartate aminotransferase (AST)	$\leq 3 \times \text{ULN}^*$	
g. Alanine aminotransferase (ALT)	$\leq 3 \times \text{ULN}^*$	

*For ALT/AST values >2 upper limit of normal (ULN) participants can only be included if bilirubin is normal.

General

16. Criterion modified per Amendment 3

16.1. Must sign an ICF indicating that the participant understands the purpose of, and procedures required for, the study and is willing to participate in the study.

17. Criterion modified per Amendment 3

17.1. Must sign a separate ICF if the participant agrees to provide an optional DNA sample for research (where local regulations permit). Refusal to give consent for the optional DNA research sample does not exclude a participant from participation in the study.

18. Must be willing and able to adhere to all specified requirements, including but not limited to completion of the required assessments, adherence to the visit schedule, and compliance with the lifestyle restrictions as specified in this protocol.

Inclusion criterion for LTE period

19. Participants are eligible for participation in the LTE period of the study if the participant:
 1. Has completed Week 52 visit of the main study, AND
has no signs and symptoms of active GCA, AND
completed treatment study intervention according to the protocol, AND
completed 26-week protocol defined GC-taper without the need to use rescue medication for GCA, AND
has not experienced a GCA flare through Week 52
 2. Has not had any study intervention-related SAE or severe AE

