9.4.5. Safety Analyses

All safety analyses will be analyzed using the Safety Analysis Set population (refer to Section 9.3 for definition).

Adverse Events

The verbatim terms used in the CRF by investigators to identify AEs will be coded using the Medical Dictionary for Regulatory Activities. Any AE occurring at or after the initial

administration of study intervention through the end of the study is considered to be treatment emergent. All reported TEAEs will be included in the analysis. For each AE, the percentage of participants who experience at least 1 occurrence of the given event will be summarized by intervention group. In addition, comparisons between intervention groups will be provided if appropriate.

The following analyses of AEs will be used to assess the safety of participants in the main study:

- Number and proportion of participants with TEAEs by treatment intervention through Week 60
- Number and proportion of participants with TEAEs by system organ class and preferred term with a frequency threshold of 5% or more by treatment intervention through Week 60
- Number and proportion of participants with treatment-emergent SAEs by treatment intervention through Week 60
- Number and proportion of participants with reasonably related TEAEs as assessed by investigator by treatment intervention through Week 60
- Number and proportion of participants with infections, serious infections, and infections requiring oral or parenteral antimicrobial treatment through Week 60
- Number and proportion of participants with TEAEs leading to discontinuation of study intervention by treatment intervention through Week 60
- Number and proportion of participants with TEAEs temporally associated with an IV infusion by treatment intervention through Week 8
- Number and proportion of participants with injection-site reactions by treatment intervention.

Summaries, listings, datasets, or participant narratives may be provided through Week 28 and Week 60 by treatment intervention, for the above AEs, deaths, and severe AEs.

Similar safety analyses from Week 52 (LTE Week 0) through Week 112 (LTE Week 60) will be performed for participants in the LTE period.

Clinical Laboratory Tests

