5.7. Safety Analyses

All safety analyses for the main study will be based on the safety analysis set based on actual intervention received, unless otherwise specified. Safety analyses for the long-term extension will include participants who complete the Week 52 visits and are assessed to be in GC-free remission with at least one SC injection at Week 52 or later.

For all continuous safety variables, descriptive statistics by intervention group will include the N, mean, standard deviation, median, minimum, and maximum. Categorical variables will be summarized by intervention group using frequency counts and percentages.

Depending on the safety data, the cumulative safety data will be analyzed through different study periods which include but are not limited to through Week 28 and through Week 60 for the main study. The safety analyses through Week 60 for the main study will include safety data through Week 60 for participants not entering the LTE and safety data through Week 52 for participants continuing onto the LTE. Safety analyses from Week 52 (LTE Week 0) through Week 112 (LTE Week 60) will be performed for participants in the LTE period.

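### The main-study safety analysis through Week 60 stops at Week 52 for LTE entrants, so the length of AE follow-up depends on outcome and will differ by arm if LTE entry does

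*SAP*

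**What the plan says.** Protocol Section 3 sets the safety endpoint as "Number/proportion of participants with treatment-emergent adverse events (TEAEs) through Week 60", and Protocol 9.4.5 repeats it as "Number and proportion of participants with TEAEs by treatment intervention through Week 60". Neither states an exception for participants who go on to the LTE. SAP 5.7 keeps the Week 60 label but defines the data as "safety data through Week 60 for participants not entering the LTE and safety data through Week 52 for participants continuing onto the LTE".

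Who gets which cut follows from the LTE rules:

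- Protocol 4.1: "Participants who complete the Week 52 visit and are assessed to be in GC-free remission, may have the option to participate".
- Protocol 5.1, criterion 19: no signs or symptoms of active GCA, taper completed without rescue, "has not experienced a GCA flare through Week 52" and "Has not had any study intervention-related SAE or severe AE". The participant must also be willing to continue.
- Protocol 4.4: the main study is complete "if a participant continued onto the LTE period, has completed main study Week 52 visit".
- Protocol 1.3, SoA footnote: those who are ineligible or decline "will continue to Week 60 visit in the main study for final safety follow up assessments".

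SAP 5.7.2 summarizes each adverse event as the count and percentage of participants with at least one occurrence, by arm. SAP 5.7.1 adds average exposure and average follow-up in weeks by arm to the safety tables. Neither document describes an exposure-adjusted rate. SAP 5.7 reports LTE entrants' safety from Week 52 to Week 112 in a separate LTE analysis.

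**The concern.** A crude percentage with at least one event grows with the time over which events are counted. In the Week 60 table, Weeks 52 to 60 count only for participants who flared, needed rescue, failed the LTE safety criterion, were otherwise ineligible, or declined. The shorter window goes to participants who did well on efficacy and had no related SAE or severe AE. That is selection on outcome, unlike a random administrative cut.

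The trial's hypothesis is that more guselkumab participants reach remission. If so, more of them are likely to enter the LTE and have their main-study window cut at Week 52. Two arms with the same underlying event rate would then show different percentages, with the better-responding arm looking slightly safer. The table label would not reveal this.

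**Working it through.** **Inputs from the documents.** Cut at Week 52 for LTE entrants and Week 60 for others (SAP 5.7). Planned arm sizes 34 and 17, and assumed Week 28 remission of 80% on guselkumab and 40% on placebo (SAP Section 3).

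**Assumptions, not in the documents.** LTE entry equals the Week 28 remission rate times an uptake fraction u. Uptake is not stated, so it is varied from 50% to 100%. Event hazard is constant and identical in both arms and in entrants and non-entrants. Early withdrawal is ignored.

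**Check on the source of the rates.** The safety section gives no figure to reproduce. The 40% and 80% come from the power calculation, which does reproduce. The pooled rate is (17×0.40 + 34×0.80)/51 = 0.667, the null SE is 0.140, the alternative SE is 0.137 and the continuity correction is 0.5×(1/17 + 1/34) = 0.044. Then Φ[(0.40 − 0.044 − 1.645×0.140)/0.137] = 82.0%, against 82% stated.

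**Mean scheduled follow-up.** Mean window = 60 − 8 × (remission rate × u) weeks.

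| Uptake | Guselkumab | Placebo | Gap |
|---|---|---|---|
| 100% | 60 − 8×0.80 = 53.6 | 60 − 8×0.40 = 56.8 | 3.2 |
| 75% | 55.2 | 57.6 | 2.4 |
| 50% | 56.8 | 58.4 | 1.6 |

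At full uptake the guselkumab window is 3.2/56.8 = 5.6% shorter. Week 52 remission may differ from Week 28. With 50% vs 20%, 60% vs 30% or 70% vs 20%, and uptake of 50% to 100%, the gap runs from 1.2 to 4.0 weeks. With equal entry in both arms it is zero.

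**Effect on a crude percentage.** For rate r per person-year, the risk by week w is R(w) = 1 − exp(−r·w/52). Each arm's expected percentage is entry × R(52) + (1 − entry) × R(60). With equal rates, the difference between arms is (0.80 − 0.40) × [R(60) − R(52)].

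| r | R(52) | R(60) | Guselkumab | Placebo | Difference (points) |
|---|---|---|---|---|---|
| 0.2 | 18.1% | 20.6% | 18.6% | 19.6% | 1.0 |
| 0.5 | 39.3% | 43.8% | 40.2% | 42.0% | 1.8 |
| 1.0 | 63.2% | 68.5% | 64.3% | 66.4% | 2.1 |

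At 50% uptake the multiplier falls from 0.40 to 0.20, and the differences become 0.5, 0.9 and 1.0 points.

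**Scale.** For 34 participants, 1.0 to 2.1 points is 0.3 to 0.7 of one person. The SE of a difference in percentages is √[p(1−p)(1/34 + 1/17)], which is 11.9 points at p = 20% and 14.6 at p = 60%. The shift is therefore about 0.1 to 0.15 SE.

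**With a common Week 52 cut.** Both arms have expected percentage R(52), so the difference due to the cut is zero at every rate and uptake.

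**The case against.** The strongest reply is that the SAP follows the protocol's own partition. Protocol 4.4 ends the main study at Week 52 for LTE entrants, and Protocol Section 3 and 9.4.5 give their later safety a separate LTE endpoint and analysis. A reader might infer that the Week 60 endpoint is not delivered, or that events drop out. The documents support neither: entrants' Week 52 to 60 events appear in the LTE analysis, and what remains is a label in Section 3 that does not mention the split.

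The plan also has mitigations. Average follow-up is displayed by arm. The Week 28 AE tables use one cut for everyone. SAP 5.7 leaves the list of analysis periods open, so a Week 52 table is already permitted. SAEs, VTEs and deaths are listed by participant. Between-arm AE comparisons are made only where appropriate, so no formal safety conclusion rests on a 1 to 2 point shift. All of this stands, but displaying follow-up does not adjust the percentages, and the Week 28 tables leave the later period without a common cut.

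A reader might also infer that guselkumab AE percentages will be biased low. That is conditional. Entrants are a subset of responders, because entry is optional and has a safety criterion, and equal entry removes the gap. Early termination also shortens follow-up and could offset it if commoner among non-responders. If entrants, selected for having no related SAE or severe AE, have a lower event rate, the effect shrinks.

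**Conclusion.** The point holds in a limited form. The main-study Week 60 safety analysis mixes two windows, and which one applies depends on efficacy and safety outcomes. If more guselkumab than placebo participants enter the LTE, the guselkumab window is shorter and its crude AE percentages are slightly understated relative to placebo. Under near-maximal assumptions (80% vs 40% entry, full uptake, equal constant hazard, no early withdrawal), the size is 3.2 weeks and about 1 to 2 points, less than one participant per arm. It is smaller with lower uptake and absent with equal entry. The net direction in the real data is not established, because early withdrawal and differing hazards are ignored here. It is unlikely to change a safety conclusion in a trial of 51, but the correction needs no new data.

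**What to change.** In SAP 5.7 and 5.7.2:

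1. Make a common Week 52 cut for the whole safety analysis set the between-arm AE comparison. Define the cut as the Week 52 visit, before the first LTE dose for entrants, so that no LTE exposure enters it.
2. Add exposure-adjusted incidence per 100 participant-years beside the percentages. This also takes account of unequal follow-up from early withdrawal.
3. Keep the Week 60 table as follow-up, with a footnote that LTE entrants contribute to Week 52 and others to Week 60, and that entrants' later events are in the LTE tables.

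Counting everyone to Week 60 should not be the main comparison. For non-entrants the last dose is at Week 48, so Weeks 52 to 60 follow the end of dosing. Entrants are dosed again from Week 52. That would set on-treatment against off-treatment time, again split by outcome. Ascertainment changes too: Protocol 8.2.8 replaces active monitoring of injection-site reactions with self-report in the LTE.

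The cost is SAP wording and one extra table or column. The drawback is that non-entrants' Week 52 to 60 events appear only in the follow-up table.

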5.7.1. Extent of Exposure

The number and percentage of participants who receive study intervention will be summarized. The cumulative dose and number of administrations of study intervention received will be summarized by treatment group for the safety analysis.

Study agent lots received by treatment, including matching placebo for active treatment will be summarized.

In addition, the average exposure (number of administrations) and average duration of follow-up (weeks) will also be summarized by treatment group in the safety tables through different study time periods.

For IV and SC study intervention:

Descriptive statistics will be presented for the following parameters:

- Number of administrations
- Cumulative total dose

Compliance to randomized intervention versus actual intervention will be presented in a summary table.

5.7.2. Adverse Events

The verbatim terms used in the CRF by investigators to identify adverse events will be coded using the Medical Dictionary for Regulatory Activities (MedDRA). Any AE occurring at or after the initial administration of study intervention is considered to be treatment emergent. If the event occurs on the day of the initial administration of study intervention, and either event time or time of administration are missing, then the event will be assumed to be treatment emergent. If the event date is recorded as partial or completely missing, then the event will be considered to be treatment emergent unless it is known to be prior to the first administration of study intervention based on partial onset date or resolution date. All reported treatment-emergent adverse events will be included in the analysis. For each adverse event, the number and percentage of participants who experience at least 1 occurrence of the given event will be summarized by intervention group.

Safety data will be summarized and displayed by the following intervention groups:

- through Week 28

1. Placebo

2. Guselkumab

In addition, overall AEs will be also summarized and displayed by the following intervention groups:

- a. Placebo IV: participants receiving placebo during the study.
- b. Placebo SC: participants receiving placebo during the study.
- c. Guselkumab — Receiving 400 mg IV Induction Doses: participants receiving at least one administration of guselkumab 400 mg IV at Week 0, 4 and 8
- d. Guselkumab — Receiving 200 mg SC Induction Doses: participants receiving at least one administration of guselkumab 200 mg SC at Week 0, 4, and 8.

- through Week 60

1. Placebo

2. Guselkumab

- during the LTE period

1. Placebo

2. Guselkumab

The following summary tables will be provided for treatment-emergent adverse events:

- AEs
- AEs with a frequency threshold of 5% or more
- Serious AEs (SAEs)
- AEs leading to discontinuation of study intervention
- AEs by severity
- AEs by relationship to each study agent within a study intervention
- AEs temporally associated with an IV infusion
- Injection-site reactions

In addition to the summary tables, listings will be provided for participants who:

- Had SAEs
- Had AEs leading to discontinuation of study intervention
- Had AEs of severity
- Had temporally associated with infusion

- Had VTEs
- Had arterial thromboembolic AEs
- Had anaphylactic reactions and serum sickness reactions
- Had suicidal ideation or suicidal behavior
- Had COVID-19 related AEs
- Had died

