Full Analysis Set with Subjects Participating in the Long-Term Extension	All participants who were in the FAS and received at least 1 injection at or beyond Week 52.
Safety Analysis Set with Subjects Participating in the Long-Term Extension	All participants who were in the safety analysis set and received at least 1 injection at or beyond Week 52.

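### SAP 5.7.2 defines the IV and SC placebo columns identically, and by default its infusion-AE table counts participants who were never infused

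*SAP*

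**What the plan says.** **Regimen columns.** SAP 5.7.2 adds a four-column display of overall AEs under the through-Week-28 heading. Column (a) is "Placebo IV: participants receiving placebo during the study" and column (b) is "Placebo SC: participants receiving placebo during the study". Apart from the label, the two are the same. Guselkumab column (c) is tied to route, dose and visits: "participants receiving at least one administration of guselkumab 400 mg IV at Week 0, 4 and 8". Column (d) does the same for 200 mg SC.

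**Infusion AEs.** The list of TEAE tables in SAP 5.7.2 includes "AEs temporally associated with an IV infusion" and gives no denominator. The general rule in SAP 5.7 is "All safety analyses for the main study will be based on the safety analysis set based on actual intervention received, unless otherwise specified". Protocol 9.4.5 asks for "Number and proportion of participants with TEAEs temporally associated with an IV infusion by treatment intervention through Week 8", also with no restriction to infused participants. Protocol 4.2 says that participants newly enrolled under Amendment 5 start on SC dosing. SAP 5.3.2.1 places IV-induction and SC-only participants in one guselkumab group.

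**LTE safety.** SAP 5.7 states: "Safety analyses for the long-term extension will include participants who complete the Week 52 visits and are assessed to be in GC-free remission", and also requires at least one SC injection at Week 52 or later. SAP Section 4 defines the LTE safety set by dosing alone: "All participants who were in the safety analysis set and received at least 1 injection at or beyond Week 52".

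**The concern.** The four-column display exists to show AEs separately for participants who started on IV dosing and those who started on SC. The IV guselkumab column then needs the placebo participants who were randomized under the same regimen and received placebo infusions. As defined, its comparator is every placebo participant, including those enrolled later who had injections only.

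This matters because the Amendment 5 summary of changes reports two venous thromboembolisms in this study during the IV induction period, and Protocol 8.3.7 now lists VTE as an event of special interest.

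A participant who never had an infusion cannot have an AE linked to one. Keeping such participants in the denominator makes a route-specific risk look smaller than it was among those exposed to it.

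The two LTE safety definitions could give different populations for the same tables.

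**Working it through.** **Inputs.** The planned arms are 34 guselkumab and 17 placebo (Protocol 9.2, SAP Section 3). The plan states no safety figure that could be reproduced. Its 82% power checks the arm sizes, which is useful because a note under SAP Table 1 gives a total of 60.

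- Difference 0.80 − 0.40 = 0.40; continuity correction 0.5 × (1/17 + 1/34) = 0.044; pooled rate (6.8 + 27.2)/51 = 0.667.
- Null SE = √(0.667 × 0.333 × (1/17 + 1/34)) = 0.140; alternative SE = √(0.24/17 + 0.16/34) = 0.137.
- Power = Φ[(0.40 − 0.044 − 1.645 × 0.140)/0.137] = 82.0%. So 34 and 17 are the sizes the plan works to.

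**Step 1: placebo columns.** Neither (a) nor (b) states a route, visit or regimen, so every placebo participant meets both definitions: 17 + 17 = 34 entries for 17 people. The number on the IV regimen is not stated. For assumed IV shares of 25%, 50%, 75% or 90%, a split by regimen would give (rounded) 4 + 13, 8 + 9, 13 + 4 or 15 + 2.

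**Step 2: infusion-AE denominator.** Let r be the rate among infused participants and s the SC-only share of the arm. With the whole arm as denominator, the reported rate is r × (1 − s). For an assumed r = 20%:

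- s = 25%: 20% × 0.75 = 15%
- s = 50%: 20% × 0.50 = 10%
- s = 75%: 20% × 0.25 = 5%

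In counts, assume that 3 guselkumab participants and 1 placebo participant had such an AE. The default table shows 3/34 = 8.8% and 1/17 = 5.9% whatever the IV share.

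| Assumed IV share | Guselkumab, infused only | Placebo, infused only |
|---|---|---|
| 25% | 3/8 = 37.5% | 1/4 = 25.0% |
| 50% | 3/17 = 17.6% | 1/8 = 12.5% |
| 75% | 3/26 = 11.5% | 1/13 = 7.7% |
| 90% | 3/31 = 9.7% | 1/15 = 6.7% |

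The understatement factor in the guselkumab arm runs from 34/31 = 1.1 to 34/8 = 4.3. The ratio between arms barely moves: (3/34)/(1/17) = 1.5 by default, and 1.4 to 1.5 among infused participants. The absolute difference does move: 2.9 percentage points by default, against 37.5 − 25.0 = 12.5 points at a 25% IV share.

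**Step 3: LTE safety.** Section 4 requires membership of the safety set and an injection at or after Week 52. SAP 5.7 adds a completed Week 52 visit and remission. Protocol 5.1, criterion 19, already requires for LTE entry no signs or symptoms, a completed taper without rescue, and no flare through Week 52. The two sets can therefore differ only for someone dosed in the LTE without meeting the entry criteria.

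**The case against.** **The labels show the intent.** The column names contain IV and SC and sit beside guselkumab columns split by route, so a programmer would probably guess what is meant. That is fair, but the labels do not settle every case. IV-induction guselkumab participants moved to SC dosing from Week 12, before the Week 28 cut. If blinded placebo followed the same schedule (an inference), participants who started on IV placebo also received SC placebo, and the label alone does not class them.

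**The scope is narrow.** This stands. A reader might infer that the SAP's safety tables in general use the wrong groups. They do not: the defect is confined to one additional display. The pooled Placebo and Guselkumab columns through Week 28, through Week 60 and in the LTE are sound for overall AEs.

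**No infusion-AE denominator is written.** This also stands. The dilution follows from the SAP 5.7 default and is not stated for this table. It would be wrong to say that the events are divided by people who never had an infusion, because the denominator would mix infused and never-infused participants. The SAP does recognise infusion exposure elsewhere: 5.7.1 reports administrations for IV and SC, and an optional analysis in 5.8.2.2 counts reactions out of all infusions. Neither sets the denominator for this table. With blocked 2:1 randomization, both arms should shrink by about the same factor, so the ratio between arms is largely preserved.

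**The VTEs are covered elsewhere.** They have their own listing and a DMC reviews safety. The documents do not name the arm of the two reported events, so they cannot be read as events on IV guselkumab. This is why a correctly defined IV placebo column is useful.

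**LTE safety.** A reader might infer that LTE safety drops participants who are not in remission. The documents do not support that. Section 4 keeps everyone dosed, the last sentence of 5.7 refers simply to participants in the LTE period, and the remission condition applies at Week 52, so later flares stay in.

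**Conclusion.** The point holds, within limits.

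- **Placebo columns:** certain from the text. The two definitions are the same, and applied literally they give 17 and 17. Only the supplementary overall-AE display through Week 28 is affected.
- **Infusion AEs:** holds as the default reading. The percentage in each arm is understated by that arm's SC-only share. The 20% rate, the event counts and all the shares above are assumptions, because the documents do not say how many participants received IV induction. Over assumed IV shares of 90% down to 25%, the factor is about 1.1 to 4.3.
- **LTE safety:** a contradiction between two SAP sections, with an expected effect of 0 to a few participants.

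No efficacy analysis and no pooled overall-AE comparison changes.

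**What to change.** 1. In SAP 5.7.2, define columns (a) and (b) by the route of placebo started at Week 0 (IV or SC induction regimen), so that each placebo participant falls in exactly one column. Copying the at-least-one-administration wording of (c) and (d) would not by itself make columns mutually exclusive, so apply the Week 0 rule to all four.
2. For the infusion-AE table, use participants with at least one IV infusion as the denominator in each arm, and print n. The matching listing needs no change, because it can contain only infused participants.
3. In SAP 5.7, replace the description of the LTE safety population with a reference to the LTE safety set in Section 4.

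The cost is about three sentences in the SAP. No new data are needed: the route of each administration is already required for the exposure summary in SAP 5.7.1.
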